5.5.3 Criteria for Causal Relationship to the Study Drug

Adverse events that fall under either "Possible" or "Probable" should be defined as "AEs whose relationship to the study drugs could not be ruled out".

Causal relationship to the study drug	Criteria for causal relationship
Not Related	A clinical event, including laboratory test abnormality, with a temporal relationship to drug administration which makes a causal relationship improbable, and/or in which other drugs, chemicals or underlying disease provide plausible explanations.
Possible	A clinical event, including laboratory test abnormality, with a reasonable time sequence to administration of the drug, but which could also be explained by concurrent disease or other drugs or chemicals. Information on drug withdrawal may be lacking or unclear.
Probable	A clinical event, including laboratory test abnormality, with a reasonable time sequence to administration of the drug, unlikely to be attributed to concurrent disease or other drugs or chemicals and which follows a clinically reasonable response on re administration (rechallenge) or withdrawal (de-challenge).

5.5.4 Criteria for Defining the Severity of an Adverse Event

AEs, including abnormal clinical laboratory values, will be graded using the National Cancer Institute (NCI)-Common Terminology Criteria for Adverse Event (CTCAE) guidelines (Version 4.03). The items that are not stipulated in the NCI-CTCAE Version 4.03 will be assessed according to the criteria below and entered into the eCRF:

Grade	Assessment Standard
1-Mild	Asymptomatic, or mild symptoms, clinical or diagnostic observations noted; intervention not indicated.
2-Moderate	Local or noninvasive intervention indicated.
3-Severe	Medically significant but not immediately life threatening, hospitalization or prolonged hospitalization.
4-Life Threatening	Life threatening consequences, urgent intervention indicated
5-Death	Death related to AE

5.5.5 Reporting of Serious Adverse Events (SAEs)

In the case of an SAE, the investigator must contact the sponsor/delegated CRO by telephone or fax immediately (within 24 hours of awareness).

The investigator should complete and submit an SAE Worksheet containing all information that is required by the Regulatory Authorities to the sponsor/delegated CRO by fax or email immediately (within 24 hours of awareness). If the faxing of an SAE Worksheet is not possible or is not possible within 24 hours, the local drug safety contact should be informed by phone.

If there are any questions, or if clarification is needed regarding the SAE, please contact the sponsor's Medical Monitor/Expert or his/her designee (see Section II).

Please fax or email the SAE worksheet for Japan (JUTOKUNA YUUGAIJISHOU HOUKOKUSHO) to:

[REDACTED]
[REDACTED]

or

[REDACTED] – Japan
[REDACTED]

Please fax or email the SAE worksheet for ROW to:

Astellas Pharma Global Development, Inc.

[REDACTED]
[REDACTED]
[REDACTED]

Follow-up information for the event should be sent promptly (within 7 days of the initial notification).

Full details of the SAE should be recorded on the medical records and on the eCRF.

The following minimum information is required:

- ISN/Study number,
- Subject number, sex and age,
- The date of report,
- A description of the SAE (event, seriousness of the event), and
- Causal relationship to the study drug.

The sponsor or sponsor's designee will submit expedited safety reports (i.e., IND Safety Reports) to the regulatory agencies (i.e., FDA) as necessary, and will inform the investigators of such regulatory reports. Investigators must submit safety reports as required by their IRB/IEC within timelines set by regional regulations (i.e., EU, eCTD, FDA). Documentation of the submission to and receipt by the IRB/IEC of expedited safety reports should be retained by the site.

The sponsor/delegated CRO will notify all investigators responsible for ongoing clinical studies with the study drug of all SAEs which require submission per local requirements of the IRB/IEC.

The investigators should provide written documentation of IRB/IEC notification for each report to the sponsor.

You may contact the sponsor's Medical Monitor/Expert for any other problem related to the safety, welfare or rights of the subject.

5.5.6 Follow-up of Adverse Events

All AEs occurring during or after the subject has discontinued the study are to be followed up until resolved or judged to be no longer clinically significant, or until they become chronic to the extent that they can be fully characterized.

If during AE follow-up, the AE progresses to an "SAE", or if a subject experiences a new SAE, the investigator must immediately report the information to the sponsor.

Please refer to [Appendix 12.2] for detailed instructions on drug-induced liver injury (DILI).

5.5.7 Monitoring of Common Serious Adverse Events

Common SAEs are SAEs commonly anticipated to occur in the study population independent of drug exposure. SAEs classified as "common" are provided in [Appendix 12.3]. The list does NOT change reporting obligations or prevent the need to report an AE meeting the definition of an SAE as detailed above. The purpose of this list is to provide an alert that some events reported as SAEs may not require expedited reporting to the regulatory authorities based on the classification of "common SAEs" as specified in [Appendix 12.3]. The sponsor will monitor these events throughout the course of the study for any change in frequency. Any changes to this list will be communicated to the participating investigational sites.

Investigators must report individual occurrences of these events as stated in [Section 5.5.5].

5.5.8 Procedure in Case of Pregnancy

If a female subject or partner of a male subject becomes pregnant during the study dosing period or within 90 days from the discontinuation of dosing, the investigator should report the information to the sponsor/delegated CRO as if it is an SAE. The expected date of delivery or expected date of the end of the pregnancy, last menstruation, estimated conception date, pregnancy result and neonatal data etc., should be included in this information.

The investigator will follow the medical status of the mother, as well as the fetus, as if the pregnancy is an SAE and will report the outcome to the sponsor.

When the outcome of the pregnancy falls under the criteria for SAEs (spontaneous abortion, induced abortion, stillbirth, death of newborn, congenital anomaly [including anomaly in a miscarried fetus]), the investigator should respond in accordance with the reporting procedure for SAEs. Additional information regarding the outcome of a pregnancy (which is categorized as an SAE) is mentioned below.

- "Spontaneous abortion" includes miscarriage, abortion and missed abortion
- Death of an infant within 1 month after birth should be reported as an SAE regardless of its relationship with the study drug
- If an infant dies more than 1 month after the birth, it should be reported if a relationship between the death and intrauterine exposure to the study drug is judged as "possible" by the investigator
- In the case of a delivery of a living newborn, the "normality" of the infant is evaluated at the birth

- Unless a congenital anomaly are identified prior to spontaneous abortion or miscarriage, the embryo or fetus should be assessed for congenital defects by visual examination

If during the conduct of a clinical trial, a male subject makes his partner pregnant, the subject should report the pregnancy to the investigator. The investigator will report the pregnancy to the sponsor/delegated CRO as an SAE.

5.5.9 Emergency Procedures and Management of Overdose

In the event of suspected ASP8273 overdose, the subject should receive supportive care and monitoring. The Medical Monitor should be contacted as applicable.

In the event of suspected erlotinib or gefitinib overdose, refer to the approved Package Insert, SPC or local product information supplied by the manufacturer for each agent.

5.5.10 Supply of New Information Affecting the Conduct of the Study

When new information becomes available necessary for conducting the clinical study properly, the sponsor will inform all investigators involved in the clinical study as well as the regulatory authorities. Investigators should inform the IRB/IEC of such information when needed.

The following 2 paragraphs are applicable to investigational sites in Japan:

1. When information is obtained regarding serious and unexpected adverse drug reactions (or other) that are specified in Article 273 of the Enforcement Regulations of the Pharmaceutical Affairs Law, in compliance with Article 80-2 Paragraph 6 of the Pharmaceutical Affairs Law, the sponsor should inform all the investigators involved in the clinical study, the head of the study site, and the regulatory authorities of such information. The head of the study site who receives such information will decide whether the clinical study should be continued after hearing the opinions of the IRB. The investigator will supply the new information to the subjects, in compliance with [Section 8.2.3.2].
2. In addition to the above item (1), when the head of the study site receives the revisions of the Investigator's Brochure, protocol, or written information, information on the matters covering the quality of the study drug, efficacy and safety, information necessary for conducting the clinical study properly, or documents to be examined by the IRB should be sent to the IRB.

5.5.11 Deviations from the Protocol and Other Actions Taken to Avoid Life-threatening Risks to Subjects (Unique to Japan)

The investigator must not deviate from or amend the protocol, excluding an emergency case for avoiding risks to the subjects. When the investigator does not follow the protocol in order to avoid urgent risks for subjects, the investigator should take the following actions.

1. Describe the contents of the deviation or amendment and the reasons for it in a written notice, and immediately send the document stating the deviation or amendment and the reasons to the sponsor and the head of the study site. Keep a copy of the notice.

2. Consult with the sponsor at the earliest possibility for cases in which it is necessary to amend the protocol. Obtain approval for a draft of the amended protocol from the IRB and the head of the study site as well as written approval from the sponsor.

5.6 Test Drug Concentration

5.6.1 Pharmacokinetics

Blood samples will be collected to analyze plasma concentrations of unchanged ASP8273 and its metabolite(s) (if applicable) in subjects randomized to the ASP8273 arm as outlined in the Schedule of Assessments. For each ASP8273 sample, 2 mL of blood will be collected in a draw tube designated for research use only and processed. Blood sampling, processing, storage and shipment instructions will be provided in the Lab Manual. Samples will be shipped to and analyzed by a sponsor-designated analytical laboratory. Please refer to the Lab Manual for more detailed information.

5.7 Other Measurements, Assessments or Methods

5.7.1 Quality of Life and Patient Reported Outcomes

Subjects will be asked to complete the QoL and PRO questionnaires electronically at baseline and at day 1 of each cycle where a visit takes place. The questionnaires should be administered prior to the start of any assessments and before the disease status is discussed with the patient. The EQ-5D-5L only will also be administered at each of the posttreatment or long-term follow-up survival contacts for 6 months after treatment discontinuation.

5.7.1.1 FACT-EGFRI-18

The FACT-EGFR-18 is a PRO instrument specifically designed to assess the effect of EGFR inhibitors on quality of life. It consists of 18 items in 3 QoL domains: symptoms, functioning and emotions.

5.7.1.2 EORTC-QLQ-LC13

The EORTC-QLQ-LC13 module items evaluate lung cancer-specific symptoms such as cough, hemoptysis, shortness of breath, sore mouth or tongue, dysphagia, tingling hands or feet, hair loss and pain.

5.7.1.3 EORTC-QLQ-C30

The EORTC-QLQ-C30 is a 30-item cancer-specific instrument consisting of 5 functional domain scales: physical, role, emotional, social and cognitive.

5.7.1.4 EQ-5D-5L

The EQ-5D-5L is a standardized instrument for use as a measure of health outcome, consisting of 6 items that cover 5 main domains (mobility, self-care, usual activities, pain/discomfort, and anxiety/depression) and a general visual analog scale for health status.

5.7.2 Biomarkers

Plasma and whole blood samples will be collected as specified in the schedule of assessments for exploratory analysis of biomarkers and EGFR mutation status. Formalin fixed paraffin embedded (FFPE) specimen, either from an archival specimen or from a recent biopsy, will be collected from all subjects. Eligibility may be determined by a previously documented EGFR mutation test result (L858R or exon 19 del). However, there should be sufficient tumor tissue from the specimen used to generate the EGFR test result to send to the central lab for confirmatory testing (10 unstained slides or FFPE block preferred, 7 slides minimum). If slides are submitted, the slides should be freshly cut from the FFPE block within 18 days of sending to the central lab. If a subject does not have a previously documented EGFR mutation test result, then a fresh formalin fixed paraffin embedded specimen (surgical resection, core needle biopsy or fine needle aspiration) must be obtained and set to the central lab for eligibility testing. Tissue slides may be retained for analysis at the central laboratory for up to 15 years.

A plasma sample for EGFR mutation detection will also be collected at baseline and at end of treatment and submitted to the central laboratory. For subjects who signed a separate ICF, an optional post-progression tumor tissue for exploratory analysis of biomarkers (e.g., EGFR mutation [T790M, C797S], c-Met mutation/amplification and AXL over expression) which are potentially related to EGFR-TKI drug response or resistance, will be collected following locally or centrally confirmed disease progression and prior to commencement of subsequent anticancer therapy.

Plasma and tissue sampling, processing, storage and shipment instructions will be provided in the lab manual. Samples will be shipped to and analyzed by a sponsor-designated analytical laboratory. Please refer to the Lab Manual for more detailed instructions.

5.7.3 Sample for PGx Substudy

PGx research may be conducted in the future to analyze or determine genes of relevance to clinical response, pharmacokinetics and toxicity/safety issues. After randomization (see Schedule of Assessments), a 4-mL sample of whole blood for possible retrospective PGx analysis will be collected and processed. Blood sampling, processing, storage and shipment instructions will be provided in the Lab Manual. Samples will be shipped to and analyzed by a sponsor-designated analytical laboratory. Please refer to the Lab Manual for more detailed information.

See [Appendix 12.4] for further details on the banking procedures.

5.8 Total Amount of Blood

The total amount of blood collected for study assessments for each subject will vary depending on how long they stay on treatment.

At any time during the study, if any laboratory abnormalities are found for a subject or for disease assessment, additional blood may be drawn for monitoring.

Additional blood beyond standard monitoring that will be drawn for this study will include draws for eligibility assessment, hematology, chemistry, and coagulation at specific study defined time points, pharmacokinetics and bioanalytical sampling.

The maximum amount of blood collected per cycle is approximately 28.2 mL in cycle 1.

6 DISCONTINUATION

6.1 Discontinuation of Individual Subject(s)

A discontinuation is a subject who enrolled in the study and for whom study treatment is permanently discontinued for any reason.

The subject is free to withdraw from the study treatment and/or study for any reason and at any time without giving reason for doing so and without penalty or prejudice. The investigator is also free to terminate a subject's involvement in the study at any time if the subject's clinical condition warrants it.

The subject will be discontinued from the treatment period if any of the following occur:

- Subject develops radiological progressive disease (i.e., PFS#1) per RECIST v1.1 based on central confirmation of investigator assessment
 - If there is radiographic evidence of PD by investigator, however the investigator believes the subject is continuing to derive clinical benefit (asymptomatic and/or without worsening of performance status or overall health) from study drug, and an increase in tumor burden is not likely to affect vital organ function, the subject may remain on study drug until the next scheduled radiographic assessment which should occur after 56 days (± 7 days).
 - If the next radiographic assessment indicates PD per RECIST 1.1 which is confirmed by the central reviewer, then the subject must be discontinued from study drug.
 - In the rare event where PD suspected on initial assessment is not confirmed on subsequent scan by the investigator or central reviewer, the subject may continue in the study.
 - The investigator should make every effort to immediately submit radiographic assessments for central review when PD is either suspected or confirmed or uncertainty exists.
 - In case of PD determination by the investigator, however not confirmed by the central reviewer, and subject is progressing clinically and requires new anti-cancer treatment immediately, the subject should be discontinued.
- Subject is required to receive local or systemic anti-cancer treatment based on investigator's clinical opinion.
- Subject develops unacceptable toxicity
- Female subject becomes pregnant

- Investigator decides it is in the subject's best interest to discontinue including clinical progression
- Requirement for significant surgical procedure; however, if surgical procedure is for the resection of the primary or metastatic lesion, the subject may be eligible to continue on study treatment after discussion with the Medical Monitor
- Significant deviation from the protocol or eligibility criteria
- Subject declines further treatment
- Subject is noncompliant with the protocol based on the investigator or Medical Monitor assessment
- Subject is lost to follow-up despite reasonable efforts by the investigator to locate the subject
- Death

The subject may be discontinued from the study if there is an interruption of treatment for > 14 consecutive days despite optimal treatment of side effects. A discussion with the Medical Monitor should occur to confirm if the subject should continue on study treatment.

Subjects who discontinue study drug and enter the posttreatment follow up period prior to reaching PFS#1 will be discontinued from the posttreatment period if any of the following occur:

- Subject develops radiological progressive disease (i.e., PFS#1) based on investigator assessment
- Subject initiates a new systemic anticancer treatment
- Subject misses 2 consecutive scheduled tumor assessments

The subject will be discontinued from the long-term follow-up period (for PFS#2) if any of the following occur:

- Subject initiates a new systemic anticancer treatment (3rd line)
- Subject exhibits evidence of PD from 2nd line therapy based on investigator assessment
- Subject declines further study participation (i.e., withdraws consent)
- Subject is lost to follow-up despite reasonable efforts by the investigator to locate the subject
- Death
- Sponsor ends long-term follow-up collection period

The subject will be discontinued from the survival follow-up period if any of the following occur:

- Subject declines further study participation (i.e., withdraws consent)
- Subject is lost to follow-up despite reasonable efforts by the investigator to locate the subject
- Death
- Sponsor ends survival follow-up period

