5.1.3 Previous and Concomitant Treatment (Medication and Nonmedication Therapy)

All medications and concomitant treatments administered from 28 days prior to cycle 1 day 1 must be recorded in the eCRF. Documentation will include the medication name, indication, route and dates of administration.

Arm A (ASP8273)

The following medications/food are likely to influence evaluation of the safety, pharmacokinetics or efficacy of ASP8273 and will be strictly prohibited:

	Prohibited Medications/Food	Reason to Exclude
1	Chemotherapy, radiotherapy, immunotherapy, or other medications intended for antitumor activity	Likely affect efficacy, safety or pharmacokinetics of ASP8273
2	Investigational products or therapy other than ASP8273	
3	Potent inhibitors (e.g., ketoconazole, grapefruit or grapefruit juice) or inducers (e.g., rifampin, phenytoin or St. John's wort) of CYP3A4	ASP8273 is a substrate of CYP3A4
4	CYP3A4 and/or P-gp substrates with a narrow therapeutic index ¹	ASP8273 may be an inhibitor of CYP3A4 and/or P-gp

¹ The drugs defined as CYP Substrates with Narrow Therapeutic Range by FDA's guidance - Guidance for Industry Drug Interaction Studies - Study Design, Data analysis, and Implications for Dosing and Labeling): <http://www.fda.gov/downloads/Drugs/GuidanceComplianceRegulatoryInformation/Guidances/UCM292362.pdf>

The use of the following medications should be avoided or used with caution and closely monitored.

	Medications to be Avoided or Used with Caution	Reason to be Cautious
1	Moderate/weak inhibitors or inducers of CYP3A4	ASP8273 is a substrate of CYP3A4
2	Inhibitors or inducers of P-gp	ASP8273 is a substrate of P-gp
3	CYP3A4 and/or P-gp substrates	ASP8273 may be an inhibitor of CYP3A4 and/or P-gp

Arm B (Erlotinib/Gefitinib)

The following medications/food are likely to influence evaluation of the safety, pharmacokinetics or efficacy of erlotinib/ gefitinib, and will be strictly prohibited:

	Prohibited Medications/Food	Reason to Exclude
All Subjects	Chemotherapy, radiotherapy, immunotherapy, or other medications intended for antitumor activity other than erlotinib/ gefitinib	Likely affect efficacy, safety or pharmacokinetics of erlotinib or gefitinib
	Investigational products or therapy	
	Potent inhibitors (e.g., ketoconazole, grapefruit or grapefruit juice) or inducers (e.g., rifampin, phenytoin or St. John's wort) of CYP3A4	Erlotinib and gefitinib are substrates of CYP3A4

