Confirmation scans for CR or PR should be done at the next scheduled assessment. If a subject discontinues study drug prior to disease progression, the subject should continue to undergo local imaging assessment every 56 days (\pm 7 days) until PD is documented per investigator, the subject misses 2 or more consecutive scheduled tumor assessments, or the subject starts another anticancer treatment, whichever occurs earlier, in order to assess PFS#1.

The site of disease progression including target, non-target and/or new lesions should be documented in the eCRF. Additional imaging may be performed at any time to confirm suspected progression of disease.

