6 ANALYSIS VARIABLES

6.1 Efficacy Endpoints

6.1.1 Primary Efficacy Endpoint

The primary endpoint is PFS assessed by the blinded IRR. For each subject, PFS is defined as the time from the date of randomization until the date of radiological disease progression (i.e., PFS#1) assessed by IRR, or until death due to any cause. If a subject has neither progressed nor died, the subject will be censored at the date of last radiological assessment or at the date of randomization if no post-baseline radiological assessment is available. Subjects who receive any further anticancer therapy for the disease before radiological progression will be censored at the date of the last radiological assessment before the anticancer therapy started. If progression or death occurs after missing 2 scheduled radiological assessments, the subject will be censored at the date of last radiological assessment or at the date of randomization if no post-baseline radiological assessment is available. Missing 2 scheduled imaging assessments is defined as the gap between two imaging assessments is more than 140 days (2.5 times the scheduled imaging assessment interval (2.5 x 56 days)).

PFS (in days) is calculated as:

(Date of death or documented Progression or censoring) – (Date of randomization) +1.

To apply the cut-off date to PFS is to exclude tumor assessments, death and anti-cancer therapy date after cut-off date in the analysis.

Note: Patient cannot be censored at "Not Evaluable (NE)". If NE is the only previous assessment, then PFS will be censored at Day 1.

Sponsor: Astellas Pharma Global Development, Inc.

ISN/Protocol 8273-CL-0302

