6.1.3 Exploratory Efficacy Endpoint

6.1.3.1 PFS on Next-line therapy (PFS#2)

PFS#2 is defined as the time from initiation of new systemic anti-cancer treatment (excluding local radiation, surgical removal of metastatic site or protocol defined Erlotinib or Gefitinib or ASP8273 based on initial treatment allocation per subject) to investigator-determined progression, discontinuation of new treatment, start of a different treatment or death from any cause, whichever comes first. Otherwise, subjects will be censored.

Subjects who have not started new systemic anti-cancer treatment will be censored at Day 1. Subjects who are alive, started new systemic anti-cancer treatment and for whom a PFS#2 event has not been observed should be censored at the last time known to be alive.

PFS#2 (in days) is calculated as:

(Date of death or investigator-determined progression on next-line therapy or discontinuation of next-line therapy or started another therapy or censoring) – (Date of randomization) +1.

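### Protocol 6.1 both stops and permits study drug when a lesion is resected, imaging-stop rules disagree, and the SAP leaves local therapy untested in PFS and without a cut-off in ORR

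*Protocol*

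**What the plan says.** **Stopping treatment.** Protocol 6.1, repeated in the synopsis under Discontinuation Criteria, lists events any one of which ends the treatment period. One is "Subject is required to receive local or systemic anti-cancer treatment" in the investigator's opinion. Another is the need for significant surgery, but, once the Medical Monitor has been consulted, "if surgical procedure is for the resection of the primary or metastatic lesion, the subject may be eligible to continue on study treatment". Radiotherapy has no such allowance: Protocol 5.1.3 strictly prohibits "Chemotherapy, radiotherapy, immunotherapy, or other medications intended for antitumor activity" during treatment.

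**Stopping scans.** For subjects off drug without PFS#1, the posttreatment list in Protocol 6.1 and its synopsis copy end follow-up when "Subject initiates a new systemic anticancer treatment". Protocol 5.3 ends imaging when PD is documented, when scans are missed, "or the subject starts another anticancer treatment, whichever occurs earlier, in order to assess PFS#1". The synopsis design overview, Protocol 2.2.1, Protocol Table 2 (footnote 1), SAP Table 2 and SAP 3.2.1 likewise stop at any other anticancer treatment.

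**Primary PFS.** SAP 6.1.1 states: "Subjects who receive any further anticancer therapy for the disease before radiological progression will be censored", at the last scan before that therapy. Protocol 7.4.1.1 agrees. SAP Table 4 uses the term 'new ACT' without defining it, and also censors a death that follows new ACT without earlier progression. PFS#2 (SAP 6.1.3.1) is counted from new systemic treatment, "excluding local radiation, surgical removal of metastatic site".

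**Response.** SAP 6.1.2.2 to 6.1.2.4 and Table 6 derive ORR, DCR and DOR without mentioning new or local therapy. Best overall response draws on all response data, ORR needs no confirmation, and ORR is in the Hochberg family with OS.

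**The concern.** Removing a tumor lesion is a local anticancer treatment. A subject who has one resected therefore meets a stop criterion and, a few bullets later, may qualify to stay on drug. Under one bullet the subject complies; under the other the subject is a reportable deviation for meeting withdrawal criteria and not being withdrawn (category PD2 in Protocol 7.8).

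The statistical consequence follows from the stay reading. On the literal PFS rule, a subject whom the protocol keeps on randomized drug stops contributing to the primary endpoint at the scan before surgery. The trial is open-label and the investigator decides on local treatment, so its use may differ by arm and the censoring may be informative. For response, nothing prevents a first PR that appears after a target lesion was cut out or irradiated from being credited to the drug in an alpha-controlled endpoint.

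**Working it through.** **1. The plan's own figure.** Inputs from Protocol 7.1: 420 events, HR 0.667, 1-sided alpha 0.025, 1:1 allocation. Schoenfeld power = Φ(½·√D·|ln HR| − 1.960). With D = 420: ½ × 20.494 × 0.4050 = 4.150; 4.150 − 1.960 = 2.190; Φ = 98.57%. The protocol says about 98.7%, so the figure reproduces. (SAP Section 4 still gives 95% for the same inputs, and SAP 7.4.1 still gives 362 events; those are separate matters.)

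**2. Effect of lost events on power.** The documents give no rate of local therapy. Assume that 1% to 10% of the planned events become censored at a fixed data cut:

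| Share lost | Events lost | Events left | Power |
|---|---|---|---|
| 1% | 4 | 416 | 98.5% |
| 2% | 8 | 412 | 98.4% |
| 5% | 21 | 399 | 98.1% |
| 10% | 42 | 378 | 97.6% |

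The analysis is event-driven, so in practice the cut-off would more likely come later.

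**3. One subject, two classifications (assumed dates).** Scans fall every 56 days, and SAP 6.1.1 counts days as date minus randomization plus 1. The second scan is at 2 × 56 + 1 = day 113 and the fourth at 4 × 56 + 1 = day 225. The lesion is resected on day 120, the subject stays on drug, and IRR progression is seen on day 225.
- Literal SAP 6.1.1: censored at day 113.
- Table 4 with 'new ACT' taken as systemic only, as PFS#2 does: event at day 225.

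On the literal reading a later death is also censored, under Table 4.

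**4. Imaging stop.** Take a subject off drug, without progression, given palliative radiation. The posttreatment list in Protocol 6.1 keeps scans going; Protocol 2.2.1, 5.3 and Table 2 stop them. Literal primary PFS is censored at the scan before radiation either way. Any later scans still enter best overall response and DOR, which have no therapy cut-off.

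**5. Response.** Protocol 5.3.1.2 defines PR as a fall of at least 30% in the sum of diameters. If a removed lesion making up 30% or more of the baseline sum were scored as zero, that alone would reach PR. With about 300 subjects per arm, each such subject moves an arm's ORR by 1/300 = 0.33 percentage points; six move it by 2 points.

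**6. Existing sensitivity analyses.** SAP 7.4.1 lists PPS, clinical progression as an event, CRF strata and restricted mean survival time. None changes how local therapy is handled.

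**The case against.** The strongest reply is that the primary rule is not split. Protocol and SAP both censor at any later anticancer therapy, which on its face includes local therapy, and Table 4 merely tabulates that text. This stands. A reader might infer that PFS#2 contradicts the primary rule, but PFS#2 is a different, exploratory endpoint that needs its own start of next-line treatment. What remains is that Table 4 does not define its term, and that the literal rule discards follow-up of subjects still on randomized drug without any analysis showing whether that matters.

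Second, the resection clause can be read as a deliberate exception to the general stop. That is plausible and the route is narrow: planned major surgery is excluded at entry, and continuing needs Medical Monitor discussion. But no precedence is stated, and if the exception governs, the censoring consequence applies directly.

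Third, a reader might infer that irradiated subjects face the same stop/stay conflict. They do not: radiotherapy on treatment is prohibited, with no stay-on-drug clause.

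Fourth, the response rules are silent rather than contradictory. No document says that the blinded reader scores an excised lesion as zero, and Appendix 12.9 has a not-evaluable row for incompletely assessed target lesions. So a surgical PR could count; it is not shown that it would.

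Fifth, the PPS may exclude subjects given prohibited anti-NSCLC treatment. That drops subjects rather than testing the alternative handling, and resection allowed under 6.1 is not clearly prohibited.

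**Conclusion.** Two contradictions are confirmed: the stop and stay bullets in Protocol 6.1, for resection only, and the imaging-stop wording in 6.1 against the other passages. Two omissions in the SAP make them matter: 'new ACT' is undefined for PFS#1 with no sensitivity analysis on local therapy, and ORR, DCR and DOR have no rule for scans after local treatment of a target lesion.

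The size cannot be computed, because no rate of local therapy is given. Under the assumed 1–10% of events, power stays above 97%, so a reader who infers a threat to power would be wrong; the concern is bias and reproducibility. A reader might also infer that resection delays RECIST progression. The documents do not settle the direction: PD is measured from the smallest sum on study, so if excision lowers the sum from 100 to 50 mm, PD needs a rise of 10 mm rather than 20 mm and could come sooner.

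**What to change.** - Reconcile the two treatment-stop bullets in Protocol 6.1 and their synopsis copies. Which one stands is the sponsor's decision.
- Use one imaging-stop wording in Protocol 6.1, 5.3, 2.2.1 and Table 2, both synopsis passages, SAP 3.2.1 and SAP Table 2. The sponsor decides which.
- In SAP 6.1.1 and Table 4, state that 'new ACT' means the same as in the text rule, and say expressly whether local radiation, resection of a metastatic lesion and resection of the primary count. The PFS#2 exclusion names only metastatic-site surgery, so copying it would leave the primary lesion open.
- Repeat PFS#1 by IRR under the other reading as a required sensitivity analysis.
- For ORR and DCR, do not count a first CR or PR recorded after a target lesion was resected or irradiated; derive DOR only from responses that count.

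The cost is SAP and amendment wording, one extra analysis run, and possibly a few subjects reclassified as non-responders. The response rule needs the treated lesion to be identifiable. Protocol 5.1.3 lists name, indication, route and dates, so the eCRF should be checked for this. The wording should be settled before treatment codes are released to the study statisticians.
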